Potentially eligible participants will be assessed via phone to determine whether they meet initial eligibility requirements. If eligible and interested, participants will be invited to Session 1 (pre Covid-19) or Session 2 (post Covid-19). They will be asked to abstain from smoking and all nicotine products (e.g., e-cigarettes) for 3 hours prior to attending this session, and told that confirmation of smoking status will be taken via a breath carbon monoxide (CO) measurement. There is no validated CO cut-off to confirm 3 hours of abstinence, so this is a “bogus pipeline” procedure, which has been found to improve accuracy of reported smoking behavior (Adams et al., 2008; Aguinis et al., 1993).

¹ Due to Covid-19 disruptions, after 3/13/20 additional safety precautions including minimizing participant contact were implemented. Aim 2 was powered for Session 2 (extinction), and cue reactivity was sufficiently demonstrated with the 17 participants who completed session 1 before the Covid-19 disruption in participant involvement. Thus, pre-Covid-19, participants attended both Sessions 1 and 2. Post-Covid-19, participants attend only Session 2 (extinction) and procedures were modified to accommodate a single session.

C.3.4. Procedure Overview for Session 1 and Session 2

At the beginning of Session 1 for pre-Covid-19 participants or Session 2 for post-covid participants, study staff will answer any questions the participants may have and the informed consent process will be completed. Participants will provide a breath CO sample and asked when they smoked their last cigarette, to confirm that they had abstained for 3 hours. Eligible participants will then complete a series of self-report questionnaires described below. We anticipate the informed consent and questionnaire phase will take approximately 45 minutes. Next, Session 1 pre-Covid-19 participants will complete the cue-reactivity procedures (about 45-60 minutes). Thus, Session 1 should take under 2 hours. Following this session, participants will be scheduled for Session 2 (extinction) within 120 days. Participants will be given similar pre-session abstinence instructions and asked to bring a pack of their own cigarettes. Again, this session will begin with self-report and CO assessment, and the full session is anticipated to last approximately 1.25 hours for pre-Covid-19 participants and 1.5-2.5 hours for post-Covid-19 participants.

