The extinction session will use only the AR cues (smoking and neutral). As noted above, participants will be randomized to either the extinction or control group. Twenty-eight trials of cues will be presented for each group. Both groups will receive the same neutral cue in Trial 1 (to establish baseline urge) and the same smoking cue in Trial 2 (for pre-test cue-reactivity). Then, the extinction group will receive smoking cues for trials 3-26, whereas the control group will receive neutral cues. Both groups will receive matched smoking cues for the second to last trial (27) followed by matched neutral cues for the final trial (28), for post-test cue-reactivity. Each cue will be presented for 1 minute and will be shown 4 times in trials 3-26. Figure 4 shows a visual representation of cue presentation for each group. With respect to the order of the cues, we will create 4 quasi-random orders for each condition (each comprising 4 blocks of 6 images, with no image repeated twice over a series of three images), which will be varied across participants. *We derived these procedures from the existing cue-exposure literature (e.g., Carpenter et al., 2009; Collins et al., 2011; Conklin & Tiffany, 2002; Kamboj et al., 2012; LaRowe et al., 2007; [name] et al., 2012), and although no specific guidelines exist, these studies typically exposed participants to cues for up to 60 minutes total (54 minutes in the current study); utilize one to nine cues (6 smoking and 6 neutral in the current study); and utilize various amounts of time for exposure to each individual cue, often ranging from 10 seconds to 5 minutes (1 minute in the current study). For this study, we wanted each cue to be presented multiple times to allow sufficient time and exposure for extinction to occur, which ultimately resulted in 28 trials.*

[figure not shown]

Figure 4: Session 2 Procedures
N = Neutral Cue; S = Smoking Cue; Dotted lines indicate paired cues

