Following each cue, participants will complete the single-item measure of urge (primary outcome). Following the final trial (28) for both groups, participants will be presented with one of their own cigarettes and asked to take at least one puff. Latency to smoke will later be determined (using time stamps on the video-recording) and used as a secondary outcome as a behavioral measure of smoking motivation (e.g., Ditre et al., 2010; Kovacs et al., 2014; Shiffman et al., 2013; Stevenson et al., 2017). TRIP is equipped with 8 “negative pressure” rooms, compliant with state law regarding indoor smoking for research purposes that allow for the efficient removal of smoke between participants. Session 2 is expected to last 1.25 hours for pre-Covid-19 participants, and 1.5 to 2.5 hours for post-Covid-19 participants.

C.3.9. Compensation and Retention

Pre-Covid-19 participants will be compensated for Session 1 (\$40) and Session 2 (\$50). Post-Covid-19 participants will be compensated \$60 for Session 2. To aid in retention, the following procedures will take place: reminder phone calls prior to all study visits, flexible scheduling for sessions, reminder cards, requiring a functioning phone number and home address to contact participants by phone or mail as needed, and obtaining the name, address, and phone number of at least 2 collaterals (i.e., relatives, friends) who can provide contact information for the participants, should we be unable to reach them during the study.

C.3.10. Additional Measures

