Three-Hour Period of Abstinence. For both studies in Aim 2, we will ask participants to refrain from smoking for 3 hours prior to the session and will rely on self-report of no smoking to gauge compliance, along with “bogus-pipeline” collection of breath CO. These decisions were made for multiple reasons. First, because participants will have a range of smoking dependence, there are no valid CO cut-points to verify abstinence within the past 3 hours. We considered adding an initial session to collect baseline CO, but this would entail participants attending 3 sessions, which would increase attrition. Second, we could have asked for overnight abstinence and confirmed abstinence with CO the following day. However, again, due to the variability in smoking dependence, CO would not be accurately captured among light smokers. Compliance with overnight abstinence would likely be lower, and we would have less flexibility for scheduling the experimental sessions. Further, the bogus pipeline of CO should further increase compliance. Third, cue-reactivity is often elevated during acute deprivation, and 3 hours of abstinence should demonstrate substantial increases in craving/withdrawal (Hendricks et al., 2006).

Modality for AR presentation. The current study will evaluate cue-reactivity and extinction via a smartphone. We also considered using headgear/eyewear (i.e., AR glasses) as another modality. On the one hand, eyewear should allow the participant to be more immersed in his/her environment with greater co-existence. However, at this time AR eyewear is extremely expensive and less scalable than if we present AR via smartphone. As such, we decided to begin this line of research using a smartphone, with the intention of testing eyewear in the future, as the technology advances and the price drops.

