The 2x2 within-subject design for Session 1 will provide measures of urge to smoke and reality/co-existence (for AR only) for analysis. Smoking cue-reactivity will be computed for both the AR and the in vivo conditions by subtracting the average urge to smoke (1-10 scale) following smoking cues from the average urge to smoke following neutral cues; higher scores represent greater smoking cue-reactivity. Based on the existing literature (Carter & Tiffany, 1999), we expect in vivo smoking cue-reactivity equivalent to a Cohen's $d = 1.0$, a very large effect. In terms of urge to smoke, this approximates an average difference score of 2.0 units with a standard deviation of 2.0.

Support for the effectiveness of AR to generate smoking cue-reactivity will be evaluated in two ways. First, average AR smoking cue-reactivity will be tested against a minimal threshold of Cohen's $d = 0.5$ (i.e., expected 1 unit on the urge to smoke scale) using a single-sample t-test. Second, the equivalence of the AR and in vivo stimuli toward generating smoking cue-reactivity will be evaluated using two one-sided tests (TOST) for equivalence.

The 142 participants completing Session 1 will be randomly assigned to the extinction or control condition in Session 2. With an estimated attrition of 10%, 128 are expected to complete Session 2. One measure of extinction will be the difference in urge to smoke at Trial 27 from urge to smoke at Trial 2, such that more positive values represent greater extinction of AR smoking cue-reactivity. Extinction based on this measure will be evaluated using a between-groups t-test. In addition, growth curve modeling will be used to compare the trajectories of urge to smoke using each self-report during the presentation of stimuli with the hypothesis of a greater negative slope for the extinction condition. Finally, the secondary measure of latency to smoke following the extinction trials will also be evaluated using a between groups t-test.

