Sample size was driven by the power required for Session 2. Power was estimated using PASS 15 (2017). With 128 participants in Session 2 (64 per condition), alpha = .05, and a two-sided test, Power will $\geq .80$ to detect a Cohen's $d \geq .50$ (a medium effect size) using the t-test. *A medium effect size is consistent with most of the existing cue-exposure treatment literature on cravings to smoke despite variations in population, types of cues (e.g., visual, audio, in vivo), number of exposures, massed or spaced exposures and number of participants. Cohen's $ds = .20, .45, .52, .75, 1.15$ for studies with reported effect sizes or with effect sizes that could be easily calculated for smoking urges (Niaura et al., 1999; Corty and McFall, 1984; Lowe et al., 1980; Kamboj et al., 2012; Unrod et al., 2014). Although an effect size was not reported, Collins et al. (2011) found significant reductions in cravings following repeated cue exposure despite having a substantially smaller sample size ($N = 42$). Studies that did not find an exposure effect were severely underpowered with Ns ranging from 7 to 32 (Götestam & Melin, 1983; Raw & Russel, 1980; Lee et al 2004; [name] et al., 2012; Miranda et al. 2008; and LaRowe et al. 2007).* Growth curve modeling of urge to smoke will have greater power presuming reliable measurement. The 142 participants completing Session 1 will yield power $> .95$ to detect a small-medium ($d = .35$) AR smoking cue-reactivity effect that is greater than the minimal threshold (1 scale unit, $d = 0.5$). This N will also yield power $> .80$ using TOST with alpha = .05 to detect an average AR reactivity within 0.25 standard deviations of the average in vivo reactivity (expected 2 scale units, $d = 1.0$).

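### Latency to smoke is compared by an unadjusted t-test although urge at Trial 2 is recorded for every Session 2 participant before the arms diverge; the test is valid, but some precision may be lost

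*Combined protocol and SAP*

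**What the plan says.** The Aim 2 part of Statistical Design and Power gives the whole latency analysis in one sentence: "Finally, the secondary measure of latency to smoke following the extinction trials will also be evaluated using a between groups t-test". It names no covariate, and no other section describes an adjusted latency analysis. The only Session 2 regressions with covariates are the exploratory moderator and mediator analyses in the same attachment.

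Section C.3.8 describes latency as timed from video after Trial 28, when participants are presented with one of their own cigarettes, and "used as a secondary outcome as a behavioral measure of smoking motivation".

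Three kinds of earlier information bear on the point:

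- **Urge before the arms diverge (C.3.8).** "Both groups will receive the same neutral cue in Trial 1 (to establish baseline urge) and the same smoking cue in Trial 2". The arms differ from Trial 3 onward, and urge is rated after every cue.
- **Stratification factors (C.3.5).** Randomisation is stratified by sex and by cigarettes per day, with a cut point of 10.
- **Time of last cigarette (C.3.4).** At the start of Session 1 (pre-Covid-19 participants) or Session 2 (post-Covid-19 participants), participants are "asked when they smoked their last cigarette, to confirm that they had abstained for 3 hours". For the pre-Covid-19 group's later Session 2, the section mentions self-report and CO without listing this question.

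**The concern.** The other Session 2 analyses use each participant's own earlier ratings: the urge measure takes the difference between Trials 2 and 27, and the growth-curve model uses every rating. Latency has no such reference. Stable differences between people in how much they want to smoke therefore stay in its error term.

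The plan treats latency as an index of smoking motivation, and it has a rating of urge to smoke taken before the manipulation. If the two are related, adjustment would narrow the confidence interval for the arm difference without recruiting anyone. What is at stake is the chance of detecting a true effect on the only Session 2 outcome that is behaviour and not a rating. The validity of the comparison is not at stake.

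**Working it through.** **Inputs from the documents** (Statistical Design and Power, Aim 2)

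- Sample size: "With 128 participants in Session 2 (64 per condition").
- Error rate: "alpha = .05, and a two-sided test".
- Effect: Cohen's d of .50 ("a medium effect size) using the t-test"), with power of at least .80.

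**Inputs that are assumptions**

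- d = .50 for latency. The plan supports this value with effect sizes for smoking urges and states no effect size or power for latency.
- R, the multiple correlation of latency with the baseline covariates within arm. The documents give no value, so a range of 0 to .5 is shown.
- A latency scale on which a linear model with roughly normal errors is reasonable.

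**Step 1: reproduce the plan's figure.** For a two-group t-test with n per arm, the noncentrality is d × √(n/2) = .50 × √32 = 2.828, with 2 × 64 − 2 = 126 degrees of freedom and a two-sided critical value of 1.979. The noncentral t distribution gives power .801, which agrees with the stated value of at least .80.

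**Step 2: adjust for baseline covariates.** The residual standard deviation is multiplied by √(1 − R²), so the standardised effect becomes .50 / √(1 − R²). Trial 2 urge, sex and cigarettes per day (two categories) take three degrees of freedom and leave 123. That cost alone is negligible: at R = 0 power is still .801.

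| R | √(1 − R²) | .50 / √(1 − R²) | Power | Unadjusted N of equal precision, 128 / (1 − R²) |
|---|---|---|---|---|
| 0 | 1.000 | .500 | .801 | 128 |
| .1 | .995 | .503 | .805 | 129 |
| .2 | .980 | .510 | .817 | 133 |
| .3 | .954 | .524 | .837 | 141 |
| .4 | .917 | .546 | .865 | 152 |
| .5 | .866 | .577 | .900 | 171 |

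With one or two covariates in place of three, the powers agree to within .001.

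**Step 3: read the gain.** At R = .2 it is .817 − .801 = .016, under 2 points. At R = .3 it is .036, at R = .4 it is .064 and at R = .5 it is .099. A gain of 5 points needs R of about .35, where power is .850.

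**Step 4: check which covariates are available.** Trial 2 urge is collected at Session 2 from everyone, on a common cue, before the manipulation. Sex and cigarettes per day must be known before randomisation. Time since last cigarette is less secure. C.3.4 itemises it at Session 1 for the 17 pre-Covid-19 participants, whose Session 2 may follow up to 120 days later. The 3-hour check that C.3.4 and C.3.5's preceding text apply at either session implies that a question is asked, but not that the number of hours is recorded. Ratings from Trial 3 onward can be affected by the manipulation and are not candidates.

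**The case against.** The strongest reply is that nothing is wrong with the planned test. In a randomised comparison an unadjusted t-test is unbiased, and its standard error already allows for chance imbalance between arms. A reader might infer that chance differences in urge or deprivation leave the latency result distorted. The documents do not support that, and this objection stands in full.

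A second reply is that the loss cannot be sized. No R is given, and d = .50 was justified for urge. A reader might take the step from .80 to .90 as the plan's own shortfall. It is a conditional illustration, and at R of .2 or less almost nothing is gained. If latency turns out skewed or bunched near zero, the tabulated gains need not apply. This also stands.

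A third reply concerns time since last cigarette. A reader might infer that it is available for everyone and should be strongly prognostic, because section C.5 says that "cue-reactivity is often elevated during acute deprivation". But that statement concerns cue-reactivity and not latency. The question's stated purpose is to confirm compliance, its recording at Session 2 is not shown for the pre-Covid-19 group, and many participants may cluster just above 3 hours. The documents do not support making it a required covariate.

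Finally, a reader might treat latency as the decisive check on the urge result. The plan calls it secondary, and the go/no-go text in C.5 does not mention it.

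None of these replies removes the narrower point: a baseline rating of the same construct is already collected from every Session 2 participant, and the latency analysis does not use it.

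**Conclusion.** The point holds as a minor matter of efficiency. The plan compares a secondary outcome that has no baseline of its own without adjustment, while Trial 2 urge is available for all Session 2 participants. There is no bias and no inflation of the error rate.

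Under the assumptions of d = .50 for latency, 64 per arm and a scale suited to a linear model, the gain in power runs from negligible (R of .2 or less) to about 10 points (R = .5). The documents do not show where in that range the trial lies. The case for the change therefore rests on its low cost more than on a demonstrated loss.

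**What to change.** In the Aim 2 part of Statistical Design and Power, replace the latency sentence with a prespecified linear model of latency on arm, adjusted for Trial 2 urge, sex and cigarettes per day (the C.3.5 stratification factors), on whatever latency scale the plan adopts. Add hours since last cigarette only if it is recorded at Session 2 for all participants. State that no rating from Trial 3 onward enters as a covariate. Keep the unadjusted t-test as a sensitivity analysis.

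The change needs a sentence or two and no new data for the core model. It uses three degrees of freedom, or four with hours since last cigarette. The downside is that it may bring little if the covariates prove weak. The covariates should be fixed before the latency data are examined, since a later choice would be open to challenge.

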We will recruit a small group of participants ($N=50$) using similar strategies and inclusion/exclusion criteria as Aim 1. *However, additional inclusion criteria will be having a smartphone that they are willing to use during the study, and being motivated to quit smoking within the next month (i.e., “preparation” stage of the Transtheoretical Model; Prochaska et al., 1992).* Because participation will be entirely remote, participants will not need to have a local address. If deemed eligible, they will be asked to provide verbal informed consent via telephone or video conferencing.

C.4.4 Procedures

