After consenting, enrolled participants will be sent a link to complete an online baseline survey. Once the completed baseline survey has been returned, the participants will be sent a code or instructions to download the free app. They will also be sent a user/training manual for the AR app use. *Given that all participants will be motivated to quit smoking, basic cessation assistance will be provided, including Tobacco Free Florida’s Quit Tips smoking cessation manual and the FL state tobacco quitline phone number and website.* A few days after the app and quitting materials are sent, research staff will call participants to explain the materials and answer questions. Participants will be instructed to use the AR app over the next 7 days in locations and situations where they smoke (e.g., home, bar; see Figure 5), with the goal of at least 5 uses per day. Usage and rating data will be collected in real-time. After the 7-day app use period, participants will be sent a link to an online follow-up survey that includes feedback on the app, smoking within the prior 7 days and smoking cessation motivation. Within approximately 7-14 days of completing the 7 day app use, participants will complete a brief telephone interview with study staff on their perceptions of the app as a potential cessation adjuvant and cigarette use over the course of the study. Participants will be compensated with electronic gift cards with value totaling up to \$80. Participants will receive \$10 for each of the completed baseline and follow-up surveys and the follow up phone interview. Participants can also receive a bonus of \$5 for each online survey completed within 24 hours of being sent the link and a bonus of \$5 if the follow up phone interview is completed within 10 days of completing the app use period. Participants will also receive \$5 for each day that they use the AR app at least one time (for up to \$35). Participants must use the app on at least four occasions to be eligible for the follow-up survey and interview.

C.4.5. Measures

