Proxies of behavior change will be collected pre- and post-app testing, including motivation to quit and self-efficacy for quitting. For motivation, we will use the Contemplation Ladder, which provides a visual image of a 10-rung ladder for participants to indicate their current motivation to change their smoking behavior (Biener & Abrams, 1991). We will also use the short form of the Abstinence-Related Motivational Engagement scale (ARME; Simmons et al., 2010), which provides a more sensitive index of current motivation. For self-efficacy, we will use the short form of the Self-efficacy Scale—Smoking, which is a 9-item measure that determines an individual’s level of confidence for not smoking in positive/social situations, negative affect situations, and out of habit (Velicer et al., 1990).

Data on smoking urges and smoking status will also be collected. Throughout testing, participants will rate their urge to smoke each time they use the app, which will allow us to observe any changes over time in this variable. Smoking status will be collected daily on the app and at follow-up, and abstinence will be defined as a self-report of no smoking in the past seven days (Perkins et al., 2013). Given the limited-time frame of this grant, we will only have short-term abstinence outcomes (7 days post-quit).

C.4.6. Statistical Considerations

See Statistical Design and Power attachment, as per new instructions for Clinical Trial applications.

C.5. Design Considerations

Choice of Comparison Stimuli Type for Aim 2, Session 1. Laboratory studies have historically used a variety of modalities for presenting cues to participants including in vivo, imaginal, video, photos, and audio (Conklin & Perkins, 2002). For this proof-of-concept study, we chose to compare the AR cues to *in vivo* cues for two reasons. First, *in vivo* cues are one of the most commonly used cues in the cue-reactivity literature (Conklin & Perkins, 2002). Second, using *in vivo* smoking cues sets the bar high for the AR comparison group, as they are the cues that smokers would typically see in their natural environment. Indeed, all other cue modalities are attempts at approximating *in vivo* cues. Thus, we believe comparing AR to real-world stimuli is ideal. Evidence that AR cues produce similar reactivity as do *in vivo* cues will provide strong support for this program of research.

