Qualitative analysis of interviews will be conducted. Interviews will be audio-recorded and verbatim transcripts created for content analysis (Charmez, 2006). Using hand coding, the goal will be to identify key themes/textual units related to the phone app. Content analysis will be conducted using an “intuitive” or “immersion/crystallizing” analysis plan, whereby the researcher reviews all data and pulls out those aspects most relevant to the research questions (Sandelowski & Barroso, 2003). The research team will identify key themes as they read through the interview transcripts. These findings will supplement quantitative data in order to identify potential changes/improvements for future iterations of the app.

Item	Scale	A Priori Benchmark
Usability and Acceptability Outcomes		
Daily use	From real-time data	≥ 80% of participants will use the app on ≥ 80% of days
System Usability Scale	Likert	≥ 80% will “strongly agree” that the app is usable (i.e., ratings ≥ 4 on 5-point scale)
Reality/co-existence	Likert	≥ 75% will rate these variables as ≥ 8 on 10-point scale
Usefulness	Dichotomous (Y/N)	≥ 75% will respond “yes”
Ease of Use	Likert	≥ 75% will indicate the app was easy to use
Ease of Learning	Days to learn (ratio); Dichotomous (Y/N)	≥ 75% will indicate 1-3 days for learning to use the app; ≤ 30% will contact staff for additional help using the app
Satisfaction	Dichotomous (Y/N); Likert	≥ 75% would recommend the app; ≥ 75% will indicate being very satisfied
Smoking Behavior		
Motivation to Quit	Contemplation Ladder/ARME	≥ 80% of the sample will increase on motivation to quit smoking
Cessation Self-Efficacy Scale	Likert Scale	≥ 80% of the sample will increase on self-efficacy for quitting
Urge to Smoke	Likert	≥ 75% of the sample will have lower urges to smoke in the last 2 days of app testing, when compared to the first 2 days of app testing
Smoking Abstinence	Dichotomous (Y/N)	None. Collected for descriptive purposes only.

Table 1. Benchmarks of Aim 3 Usability and Acceptability Testing.

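### The Aim 3 urge benchmark ignores smoking status during the app week, so stopping between its two windows can be scored as a failure

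*Combined protocol and SAP*

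**What the plan says.** - **Benchmark.** The urge row of Table 1 (Statistical Design and Power) requires "≥ 75% of the sample will have lower urges to smoke in the last 2 days of app testing". The reference is the participant's own urge over the opening 2 days. Neither the row nor the Aim 3 text above it mentions smoking status. Abstinence has no benchmark of its own.
- **Who enters.** Section C.4.3 recruits a single group of 50 and adds "being motivated to quit smoking within the next month" as an entry criterion.
- **What happens in the week.** Under C.4.4, "basic cessation assistance will be provided" to everyone (a quit manual and quitline details). Also: "Participants will be instructed to use the AR app over the next 7 days in locations and situations where they smoke", with a goal of at least 5 uses a day. No quit date is set inside those 7 days.
- **What is measured.** Under C.4.5, urge is rated at every app use, and "Smoking status will be collected daily on the app and at follow-up". Abstinence is defined as self-reported non-smoking over the past seven days.
- **Abstinence and craving.** C.5, explaining the pre-session rule for Aim 2, states that "3 hours of abstinence should demonstrate substantial increases in craving/withdrawal" and that cue-reactivity is often raised in acute deprivation. Aim 2 therefore asks for 3 hours without smoking and reschedules anyone who reports otherwise (C.3.4). Aim 3 has no such standardisation.
- **Consequence.** The Aim 3 statistical text says that missed benchmarks lead to adjustment of the app and re-testing in later studies. It also lists urge among the descriptive outcomes for which the study is not powered.

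**The concern.** The urge comparison is within person, over one week, without a control group. Two things can move it: any extinction produced by the app, and any change in the participant's smoking. On the protocol's own premise that short abstinence raises craving, a person who stops after the first window and before the last may report higher urges at the end even if the app works. The benchmark then records a failure that reflects withdrawal.

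The opposite case also exists. Someone abstinent from day 1 carries withdrawal in both windows. If craving fades over the week, that person is pushed toward a pass whatever the app does.

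At stake is how the pilot result is read. A missed benchmark could come from quitting or from no urge reduction, and the planned summary cannot tell these apart although the data to do so are collected.

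**Working it through.** The 75% threshold is asserted in Table 1 without a derivation, so there is no calculation to reproduce. The check asks how sensitive it is to stopping during the week.

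**Inputs from the documents:** N = 50 (C.4.3); threshold 75%, days 6-7 against days 1-2 (Table 1); 7 days and a goal of 5 uses a day (C.4.4).

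**Assumptions, none given in the documents:** share q who stop mid-period; their chance p_q of a lower last-window urge; the chance p_s = 0.80 for continuing smokers; and all 50 giving ratings in both windows.

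**Step 1, number needed.** 0.75 × 50 = 37.5, so 38 must pass (38/50 = 76%) and 12 may fail.

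**Step 2, pass rate needed among the rest.** (38 − 50·q·p_q) / (50 − 50·q).

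**Step 3, chance of meeting the benchmark.** P(X ≥ 38) for X binomial with n = 50 and p = q·p_q + (1 − q)·0.80.

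| q | p_q | Needed among the rest | p | Chance of meeting |
|---|---|---|---|---|
| 0 | – | 38/50 = 76% | 0.80 | 0.81 |
| 10% | 0 | 38/45 = 84% | 0.72 | 0.33 |
| 10% | 0.5 | 35.5/45 = 79% | 0.77 | 0.64 |
| 20% | 0 | 38/40 = 95% | 0.64 | 0.05 |
| 20% | 0.5 | 33/40 = 82.5% | 0.74 | 0.45 |
| 20% | 0.75 | 30.5/40 = 76% | 0.79 | 0.76 |

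If 13 of 50 (26%) stop and none passes, only 37 remain and the benchmark cannot be met. If stoppers pass at 75%, little changes.

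**Step 4, day of stopping.** Assume a linear urge decline of D points from day 1 to day 7, a between-day SD of 1.0, a within-day SD of 1.5 and 5 ratings a day.

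- The window midpoints are 5 days apart out of 6, so the expected fall is (5/6)·D.
- Variance of a daily mean: 1.0² + 1.5²/5 = 1.45. Each window averages two days (0.725), so the difference has variance 1.45 and SD 1.204.
- Chance of a pass = Φ[((5/6)·D − r)/1.204], where r is the withdrawal effect in the last window minus that in the first.

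| Case | D | r | Chance of a pass |
|---|---|---|---|
| Keeps smoking | 1 | 0 | 0.76 |
| Stops on days 3-6, lasting 1-point rise | 1 | 1 | 0.44 |
| Stops on days 3-6, lasting 2-point rise | 1 | 2 | 0.17 |
| Stops on day 1, lasting rise | 1 | 0 | 0.76 |
| Stops on day 1, 1-point rise fading 20% a day | 1 | −0.605 | 0.88 |
| Stops on day 1, 2-point rise fading 20% a day | 1 | −1.21 | 0.96 |
| Stops on days 3-6, lasting 1-point rise | 2 | 1 | 0.71 |

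For the fading 1-point rise, the first window averages (1 + 0.8)/2 = 0.90 and the last (0.8⁵ + 0.8⁶)/2 = 0.295, so r = −0.605. The 2-point case doubles this.

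The penalty therefore attaches to stopping between the windows, not to stopping as such.

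**The case against.** A reader might infer that entrants are on the point of quitting, that the protocol says abstinence raises craving, and hence that people who stop smoking tend to fail the benchmark. The documents do not support that much.

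- **Timing.** The entry criterion is an intention within a month, and participants are told to use the app where they smoke. If quit days were uniform over 30 days (an assumption), 5/30 = 17% would fall on days 3-7.
- **Craving.** The C.5 statement concerns 3 hours of deprivation before a laboratory session. It gives neither a size on the urge scale nor a course over days. Entry criteria are similar to those of Aim 1, which admits people smoking 3 cigarettes a day, and they may have gaps that long in both windows while still smoking.
- **Direction.** Stopping on day 1 is neutral or favourable, and stopping after day 7 has no effect.
- **Size.** The 84% and 95% figures assume that every stopper fails, which is the worst case.
- **Consequence.** The adjust-and-retest sentence follows one about usability and acceptability benchmarks. Table 1 places urge under a separate smoking-behaviour heading. The table's caption makes it arguable that the rule reaches urge, but not certain.

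All of this stands and sets the limits of the point. It does not remove it: the row pools people whose smoking changed with people whose smoking did not, on an outcome that the protocol itself treats as sensitive to recent smoking. The seven-day abstinence definition does not help either. Someone who stops on day 4 and stays abstinent can meet it by the interview 7-14 days after app use, yet still be scored an urge failure.

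**Conclusion.** The point holds in a limited form. The urge benchmark takes no account of change in smoking during the app week. A participant who stops between the first and last 2 days may be scored a failure because of withdrawal; one abstinent in both windows is not penalised and may be favoured.

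Size and direction depend on quit timing and the course of craving, which the documents do not give. Under assumed stopping rates of 10% to 20%, the pass rate needed among the rest rises from 76% to 84-95% if no stopper passes, or to 79-82.5% if half do. It hardly moves if stoppers pass at 75%.

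It would go too far to say that quitters in general count as failures, or that the plan would certainly rework the app because of this row. Aim 3 is a descriptive pilot, so what is affected is interpretation of one benchmark, not a formal test.

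**What to change.** Keep the whole-sample figure in the Table 1 urge row as the benchmark. Beside it, report the proportion with lower urge in the last window by the daily smoking status that the app already records:

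1. smoking in both windows;
2. stopped between the windows, with the day of stopping;
3. abstinent in both windows.

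State in the Aim 3 text that a met or missed urge benchmark will be read against this split before it is attributed to the app.

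The cost is a few extra lines of output, with no new data collection. The subgroups will be small, and they are defined by something that happens after baseline, so the split is descriptive and should not replace the whole-sample figure. Restricting the benchmark to people smoking in both windows would drop those who quit, possibly the best responders. Daily status also cannot pick up cutting down, or smoking just before an app session, so some of the ambiguity will remain.
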